7.1 Sample Size Determination

We calculated power for comparing groups on change in SRS-2 total score (the primary outcome measure), using a standard approach for linear mixed models (Littell RC, Milliken GA, Stroup WW, Wolfinger RD, Schabenberger O. *SAS for mixed models [electronic resource]*. Cary, N.C.: SAS Institute, Inc.; 2006). We assumed that the mean differences observed in the trial by Singh et al. represented the true values (i.e., we assumed mean differences of 7, 20, 18.4, and 0.4 at weeks 4, 8, 12 and 16, respectively), and we assumed a constant standard deviation of 20, consistent with that observed by Singh et al. Furthermore, we assume within-participants across time correlation of 0.5 (a conservative value) and we assume no more than 15% loss distributed over the 16 weeks of follow-up. Under these assumptions, randomizing 27 participants to each group will provide at least 80% power for an overall test comparing groups across all time points using a two-sided 4 degree of freedom test at the 0.05 significance level.

For the exploratory microbiota analysis, we aim to include a subset of 30 subjects in the sample. In a recent randomized cross-over trial of the effects of broccoli consumption on microbiota composition in 18 healthy adults [Kaczmarek 2017*], participants consuming broccoli exhibited an increase in the ratio of Baceteroidetes to Firmicutes by 37% from baseline to end, compared to a 5% reduction during the control period (p=0.02). With 15 participants per group, we will have >80% power to detect a similar change in the ratio of Bacteroidetes to Firmicutes.

* Kaczmarek JL, et al. Broccoli consumption impacts the human gastrointestinal microbiota. The FASEB Journal, 2017. 31(1 suppl): p.965.

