Sulforaphane (SF), derived from freeze-dried broccoli sprouts, was recently investigated as a treatment for symptoms of ASD in a randomized, double-blind, placebo-controlled trial of 45 male adolescents and young adults (ages 13-30 years old) with moderate to severe autism (clinical trials identifier NCT01474993) [48]. Fifteen participants were randomized to placebo and 29 to SF: each group was treated for 18 weeks, followed by a 4-week discontinuation period and final follow-up at 22 weeks. Forty participants (14 on placebo, 26 on SF) completed the trial; of those participants, 32 (80%) had a reported history of behavioral improvement during fever episodes. The primary outcome was change in symptoms of autism as measured by change in Social Responsiveness Scale (SRS) total scores; additional measures of interest included change in caregiver-completed Aberrant Behavior Checklist (ABC) scores and clinician-rated Autism Clinical Impressions Severity and Improvement Scales (OACIS-Severity and OACIS-Improvement). SRS scores improved significantly more in the SF group compared with the placebo group (-15 units vs -3 units; p=0.02). Considering the 4 non-completers as non-responders, 31% (9/29) SF participants vs 0% placebo participants demonstrated a 25% decrease in total SRS score from baseline (p=0.018). SF participants also demonstrated significantly greater improvement in ABC total and OACIS-Improvement scores, particularly in the domains of social interaction (p=0.003), aberrant/ abnormal behavior (p=0.007), repetitive/ stereotypical behavior (p=0.08), and verbal communication (p=0.008). SF was well-tolerated with no serious adverse events. Two subjects

with a history of seizures had single unprovoked seizures during the course of the study (one after 3 weeks on SF, one 3 weeks after discontinuing SF), and the possibility of seizure as potentially associated with SF could not be ruled out.

Based on available data from Phase I human clinical trials of SF-rich compounds, SF appears to be extremely well-tolerated with minimal risk aside from mild gastrointestinal symptoms, which may include bloating, nausea, and loose stools.

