1.4 Dose Rationale and Risk/Benefits

The Avmacol[®] dosing regimen for the current study was designed to deliver a slightly higher concentration of SF as that administered in a previously reported clinical trial of SF for ASD [48]. In the randomized, placebo-controlled trial by Singh et. al [48], participants randomly assigned to the active treatment group received capsules containing SF-rich broccoli sprout extracts that provided approximately 50 µmol SF/cap. Dosing was weight-based as follows:

50 μ mol SF (1 cap) daily for weight < 100 100 μ mol SF (2 caps) daily for weight 101-199 lb. 150 μ mol SF (3 caps) daily for weight ≥ 200 lb.

Using this dosing schedule, participants receiving SF demonstrated significant improvement in social impairment as measured by change in Social Responsiveness Scale (SRS) total scores and significant improvement in related challenging behaviors as measured by the Aberrant Behavior Checklist (ABC) as compared with placebo over the course of the 16-week active treatment period. Between group differences were first observed by week 4 of treatment. These doses of SF were well-tolerated by participants and were not significantly associated with adverse events, change in blood pressure or heart rate, or change in routine laboratory values. Unexpectedly, SF treatment was associated with minor but significant weight gain, and 2 participants with a history of seizures had single, unprovoked seizures (one taking SF, one taking placebo).

The currently proposed clinical trial is designed to independently replicate the study by Singh and colleagues [48], to support or refute these findings. Avmacol® delivers SF in the form of its glucosinolate precursor, glucoraphanin (GR; derived by broccoli seed extract), and the active enzyme myrosinase (derived from broccoli sprouts), which hydrolyzes GR to SF upon ingestion. Bioavailability studies have demonstrated approximately 40-50% endogenous conversion of GR to SF upon ingestion of compounds containing GR enriched with myrosinase in healthy participants [47]. Each tablet of Avmacol®, formulated for use in clinical trials, contains approximately 15 mg (34.4 μ mol) of glucoraphanin. Assuming 45% endogenous conversion of GR to SF (which will vary somewhat from individual to individual), each tablet will therefore supply approximately 15.5 μ mol SF/tablet. The weight-based Avmacol®/ placebo dosing schedule for the current study is as follows:

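### The SRS differences behind the sample size are attributed to the earlier autism trial but are not reconciled with the 12-point result and treatment length the protocol reports for that trial

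*Combined protocol and SAP*

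**What the plan says.** Section 7.1 takes the mean differences observed in the earlier autism trial as the true values. It lists them ("we assumed mean differences of 7, 20, 18.4, and 0.4 at weeks 4, 8, 12 and 16, respectively"), adds "we assumed a constant standard deviation of 20", described as consistent with the same trial, and assumes a within-participant correlation of 0.5 and at most 15% loss over 16 weeks. With 27 per arm, its conclusion is that this sample "will provide at least 80% power for an overall test comparing groups across all time points". The test behind that claim has 4 df and a two-sided 5% level.

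The protocol describes that trial in two other places:

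- **Clinical Data to Date (after section 1.3).** SRS change was −15 on sulforaphane and −3 on placebo ("15 units vs -3 units; p=0.02", the first figure also being a decrease). The sentence names no visit. On design: "each group was treated for 18 weeks, followed by a 4-week discontinuation period and final follow-up at 22 weeks".
- **Section 1.4.** Improvement on sulforaphane is described "over the course of the 16-week active treatment period". Appendix 6B also gives 16 weeks.

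In the present trial, treatment ends at week 12 and week 16 follows four weeks off drug.

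**The concern.** Two things do not fit.

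**Size.** Differences of 20 and 18.4 are presented as observed in a trial whose SRS result the protocol reports as 12 points. Nothing says how the figures relate.

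**Timing.** Whether the earlier trial treated for 16 or 18 weeks, its participants had not been off drug for four weeks at week 16. A near-zero on-treatment difference at week 16 would clash with the benefit that section 1.4 describes, and section 7.2 expects the difference to disappear after discontinuation. The 0.4 is therefore best read as a later off-drug value placed on this trial's calendar. If so, the 18.4 at week 12 may also come from a later visit and reflect more than 12 weeks of treatment.

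Section 7.1 contains the only power argument for 54 participants. Section 1.4 says the trial is meant to support or refute the earlier findings. How much a null result can say against them depends on the power for the effect that was actually seen.

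**Working it through.** **Inputs.** Section 7.1: d = (7, 20, 18.4, 0.4), SD 20, correlation ρ = 0.5, 27 per arm, 15% loss (27 × 0.85 ≈ 23), two-sided α 0.05, 4 df. Clinical Data to Date: 15 − 3 = 12 points. My assumptions: compound symmetry, and loss bracketed by n = 27 (none) and n = 23 (all 15% lost at the start).

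**Formula.** With n analysed per arm, λ = (n/2)·q, where

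q = [Σd² − ρ(Σd)²/(1 + 3ρ)] / [SD²(1 − ρ)].

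At ρ = 0.5 and SD 20 this is q = [Σd² − 0.2(Σd)²]/200. Power comes from the noncentral F with (4, 2n − 5) df. The 5% critical values are 2.561 for n = 27 and 2.600 for n = 23.

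**Step 1: the plan's own figure.** Σd² = 787.72 and Σd = 45.8, so q = (787.72 − 419.53)/200 = 1.841.

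- n = 27: λ = 13.5 × 1.841 = 24.85, power 98%.
- n = 23: λ = 11.5 × 1.841 = 21.17, power 95%.

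Spreading the loss evenly over the visits gives λ = 22.4 and power of about 96.5%. The stated lower bound of 80% holds with a wide margin; 16 analysed per arm would already exceed it.

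**Step 2: the protocol's 12-point figure, SD 20.** The documents do not say where in the profile 12 belongs, so three placements are shown.

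| Profile (weeks 4, 8, 12, 16) | q | λ, n = 27 / 23 | Power, n = 27 / 23 |
|---|---|---|---|
| Whole profile × 12/18.4: 4.57, 13.04, 12, 0.26 | 1.841 × (12/18.4)² = 0.783 | 10.57 / 9.01 | 70% / 61% |
| Weeks 8 and 12 at 12: 7, 12, 12, 0.4 | (337.16 − 197.19)/200 = 0.700 | 9.45 / 8.05 | 64% / 55% |
| Only week 12 at 12: 7, 20, 12, 0.4 | (593.16 − 310.47)/200 = 1.413 | 19.08 / 16.26 | 93% / 88% |

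**Step 3: baseline adjustment.** Section 7.2 includes a pre-treatment SRS-2 covariate. Adjusting for one baseline score at ρ = 0.5 raises the three rows to about 69–78%, 65–75% and 93–97%. The first two stay below 80%.

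**Step 4: the calendar.** Last treatment week of the earlier trial: 18 (Clinical Data to Date) or 16 (section 1.4). Four weeks off drug is then week 22, as the protocol states, or week 20. Neither is week 16.

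**The case against.** The power statement is a lower bound and it is met. A reader might infer from the mismatch that 80% is miscalculated. It is not: the stated inputs give 95–98%, and moving week 12 alone to 12 still leaves 88–93%.

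A contradiction between 12 and 18.4 is also not proven. A reader might take the 12 points as the result after 18 weeks, but the sentence gives no visit. The 12 could belong to another visit or be an average over visits (45.8/4 = 11.45 for the four planning differences). It could also be a difference in change from baseline, with 18.4 a difference in raw means. Only the cited paper could settle this.

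A further tempting step is to say that 12 points, SD 20 and p = 0.02 are incompatible. An unadjusted t-test on the 14 and 26 completers would give t = 12/[20√(1/14 + 1/26)] = 1.81 and p = 0.078. But the documents name no test and do not say whether SD 20 is for raw or change scores. If it is for raw scores and the correlation is 0.72, the change SD is 20√(2 × 0.28) = 15.0, close to the 14.9 that p = 0.02 would need. With SD 15, the profile scaled to 12 points has 93% / 87% power.

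The correlation of 0.5 is not a problem either: at 0.25 the stated inputs still give 96% / 92%. Section 7.2 also promises estimates with 95% intervals, so a null result need not be read from the p-value alone.

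All of this stands, and it limits the point to undocumented and unreconciled inputs. It does not remove it. Each explanation depends on a visit or scale that section 7.1 leaves out, and they lead to quite different power.

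**Conclusion.** The planning differences are attributed to one trial, do not match the protocol's own report of that trial, and carry at least one week label that cannot be literal. The power claim is correct for the inputs as written (about 95–98%). With 12 points and SD 20 it is about 61–70% for the scaled profile, 55–64% with weeks 8 and 12 both at 12, and 88–93% with only week 12 at 12.

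These figures assume compound symmetry, correlation 0.5, 23 to 27 analysed per arm and no baseline adjustment. Where the 12 belongs is also an assumption. That 18.4 reflects more than 12 weeks of treatment is possible but not shown. The documents do not establish that the trial is underpowered; they do not allow a reader to tell.

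**What to change.** In section 7.1:

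1. For each planning difference, give the visit of the earlier trial it came from, whether it is on the raw or change scale, and whether participants were on or off treatment. Give the scale of SD 20.
2. Reconcile these with the 12-point result in Clinical Data to Date, and reconcile the 18-week and 16-week descriptions of that trial.
3. Replace the power statement with the power from that one consistent set of inputs, and state the power at a 12-point difference beside it.

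This takes a recalculation and a few sentences, with no change in enrolment. The cost is that the stated power may become less favourable.

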If the dose is reduced during the course of the study, the participant will continue the lowered dose for the remainder of the study. If adverse events do not improve within 14 days of lowering the dose, the investigational product may be permanently discontinued at the discretion of the treating study physician, participant, and participant's guardian. If a participant exhibits extreme exacerbation of behavioral symptoms (such as self-injurious behavior or aggression) that do not improve substantially following a dose reduction and are determined "probably" or "definitely" related to taking the investigational product, the investigational product may be permanently discontinued sooner than 14 days post-reduction, and the DSMB will be notified. As individuals with ASD often have cyclical changes in behavior independent of medication effects, the study staff will rely on caregivers' experience with the participant to determine if any observed behavior changes are within the expected range for that individual. If the investigational product is stopped permanently, the participant and his caregiver will be asked to complete the remainder of the study visits, return any unused study drug, and repeat safety lab studies.

2 Study Objectives

Primary Objective:

The primary objective of this clinical trial is to determine if Avmacol[®] is superior to placebo for improving social communication impairment in adolescent and young adult men with moderate to severe autism spectrum disorder (ASD), as measured by change in Social Responsiveness Scale-2 (SRS-2) [100] total scores.

Secondary Objectives:

Secondary objectives include: (1) assessing the safety and tolerability of Avmacol[®] in subjects with ASD; and (2) characterizing the effects of Avmacol[®] on behavioral challenges commonly associated with ASD, including hyperactivity, irritability, repetitive behavior, and inappropriate speech.

Exploratory Objectives:

In a subset of 30 participants, exploratory objectives include: (1) Assessment of gut micobiota diversity and relative abundance of microbial species from fecal samples collected before and after 12 weeks of treatment with sulforaphane or placebo. (2) Explore the relationship between changes in microbiota composition and behavioral outcomes in young men treated with sulforaphane or placebo.

3 Study Design

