3.1 General Design

We propose to conduct a Phase II, randomized, double-blind, placebo-controlled trial of Avmacol®, a rich source of sulforaphane, for the treatment of social impairment in individuals with ASD. Fifty-four male subjects with autism spectrum disorder (ASD) between ages 13 and 30 years old will be randomized in a 1:1 ratio, stratified by age category (13-18 and 19-30 years old), to receive either Avmacol® or identical placebo tablets. Participation will be limited to males to closely approximate the sample used in the SF for ASD clinical trial by Singh et al. [48] and to account for possible mechanistic differences in ASD between males and females (ASD is 4 times more common in males). Stratification by age will account for possible age-based differences in response to treatment (adolescence vs. adulthood) and allow for secondary analysis by age group (adolescent vs. adult).

The length of study participation from baseline to study termination for each individual subject is 16 weeks, including a 12-week active treatment phase (Avmacol® or placebo), followed by a 4-week blinded discontinuation phase. Participants will be monitored with clinic visits at regular intervals (baseline and weeks 4, 8, 12, and 16) for improvement in a well-characterized, caregiver-rated measure of social impairment (Social Responsiveness Scale-2 (SRS-2) [100], the primary outcome) as well as secondary measures of (1) repetitive behaviors associated with ASD (Repetitive Behavior Scale- Revised; RBSR) [102]; (2) challenging behaviors commonly associated with developmental disabilities (Aberrant Behavior Checklist; ABC) [103]; (3) clinician-rated functional severity (Clinical Global Impression Scale- Severity; CGI-S) [104]; and clinician-rated functional improvement (Clinical Global Impression Scale- Improvement; CGI-I) [104].

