Similar GLMM analyses will be conducted to examine the longitudinal assessments of CGI Severity and RBSR and of subscales if the total scores show treatment impacts.

Exploratory Hypotheses

We hypothesize that treatment with sulforaphane will result in greater diversity of gut microbial species and a higher ratio of Bacteroidetes to Firmicutes spp. compared to placebo, and that these alterations in gut microbiota will be positively associated with behavioral improvements in the sulforaphane treatment group.

We will utilize Genotek's validated wet-lab and metagenomic data analytic pipeline for the batched sample processing and data analysis. Microbial DNA will be extracted and amplified using PCR, and 16S rRNA gene sequencing will be performed using the Illumina MiSeq platform. A curated taxonomic database will be used to assign a taxonomic classification to the sequencing reads. The mean (%) relative abundance of microbial phyla and genera will be calculated for the sulforaphane and placebo groups pre- and posttreatment. The percent change in Bacteroidetes to Firmicutes (B:F) ratio from baseline to endpoint will be compared between treatment groups using Analysis of Covariance (ANCOVA), with baseline B:F ratio included as a covariate.

Microbiota diversity and relative abundance will be assessed using conventional within sample ("alpha diversity") and between-sample ("beta diversity") metrics. Three metrics will be used to assess change in alpha diversity over time: the absolute number of operational taxonomic units (OTUs), Chao1 estimator, and Shannon index. We will use ANCOVA to test for significant differences in alpha diversity from baseline to endpoint within each treatment group. Beta diversity will be assessed with 3 metrics: Bray-Curtis dissimilarity, Weighted Unifrac distance, and Unweighted Unifrac distance. These indices will be used to determine the variance in an individual over time and the mean dissimilarity between individuals in each group. Weighted Unifrac distance distance will be used for Principal Coordinates Analysis (PCoA). We will create a PCoA plot to visually identify whether samples from each treatment group cluster together at different time points (before and after treatment). This can help determine whether any changes identified during beta diversity analysis are directed changes or random noise.

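### Is the >80% power stated for the exploratory Bacteroidetes-to-Firmicutes comparison (15 per group) wrong, given the crossover result it cites?

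*Combined protocol and SAP*

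**What the plan says.** Section 7.1 has two power statements. The first, for the SRS-2 total score, gives its inputs: mean differences by week, an SD of 20, a correlation ("we assume within-participants across time correlation of 0.5 (a conservative value"), 15% loss and a two-sided 0.05 test.

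The second concerns the microbiota subset, where "we aim to include a subset of 30 subjects in the sample". Its basis is a published abstract: "In a recent randomized cross-over trial of the effects of broccoli consumption on microbiota composition in 18 healthy adults", in which the Bacteroidetes-to-Firmicutes (B:F) ratio rose "by 37% from baseline to end, compared to a 5% reduction during the control period (p=0.02"). The conclusion is "With 15 participants per group, we will have >80% power to detect a similar change in the ratio of Bacteroidetes to Firmicutes". No SD, correlation, covariate gain or loss is given for B:F.

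Section 7.2 (Exploratory Hypotheses) sets the analysis: the percent change in the B:F "ratio from baseline to endpoint will be compared between treatment groups using Analysis of Covariance (ANCOVA), with baseline B:F ratio included as a covariate". Section 3.1 makes this a parallel-group comparison: participants "will be randomized in a 1:1 ratio, stratified by age category". Section 2 places the microbiota work among the exploratory objectives: "In a subset of 30 participants, exploratory objectives include" microbial diversity and its relation to behaviour.

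**The concern.** A crossover p-value reflects how much a person's two period changes differ from each other. A parallel-group comparison depends on how much changes vary between people. To move from one to the other you need the correlation between the two changes, and the plan gives none for B:F. It also does not say how much variance the baseline covariate is expected to remove. The preceding paragraph supplies an SD, a correlation and a loss rate for SRS-2, so their absence here is noticeable.

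The simplest conversion (independent changes, no covariate gain) gives about 62% power rather than more than 80%. If that were the whole story, the subset of 30 would rest on an overstated figure, and a null B:F result could be read as stronger evidence against a 42-point difference than it is.

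**Working it through.** **Can the figure be reproduced?** Not from the plan's own inputs, since no SD is stated. It can only be approached by working back from p=0.02.

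**Inputs from the documents.** Difference 37 − (−5) = 42 percentage points; n = 18 in the crossover; p = 0.02; 15 per group; ANCOVA with baseline B:F (sections 7.1 and 7.2).

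**Assumptions not in the documents.** p = 0.02 is two-sided and from a paired t-test on the 42-point difference; the B:F test is two-sided at 0.05; the correlation ρ between a person's two period changes and the share of variance R² explained by baseline are shown as ranges.

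**Step 1: SD of the within-person difference.** t(0.99, 17 df) = 2.567, so SD = 42 × √18 / 2.567 = 69.4 points.

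**Step 2: SD of a single change.** SD = 69.4 / √(2(1 − ρ)), giving 43.9, 49.1, 56.7 and 69.4 at ρ = −0.25, 0, 0.25 and 0.5.

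**Step 3: power at 15 per group.** Noncentral t with noncentrality 42 / (SD × √(1 − R²) × √(2/15)); 28 df unadjusted, 27 df for ANCOVA.

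| | ρ = −0.25 | ρ = 0 | ρ = 0.25 | ρ = 0.5 |
|---|---|---|---|---|
| Unadjusted (not the planned test) | 72% | 62% | 50% | 36% |
| ANCOVA, R² = 0.25 | 83% | 74% | 62% | 45% |
| ANCOVA, R² = 0.36 | 88% | 81% | 69% | 52% |
| ANCOVA, R² = 0.50 | 95% | 89% | 79% | 62% |
| R² needed for 80% | 0.19 | 0.35 | 0.51 | 0.68 |

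Put another way, 80% power under ANCOVA needs a residual SD of about 39.6 points, or a difference of 42 / 39.6 = 1.06 residual SDs.

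**Step 4: which cells are plausible?** Section 7.1 describes change from baseline to end, set against change during the control period. If each period had its own baseline (an assumption), equal correlation among a person's four measurements gives ρ = 0. Correlation that decays over equally spaced measurements (AR(1), with r between neighbours) gives ρ = −r(1 − r)/2, which is slightly negative. The ρ = 0.5 column fits a single shared baseline, which the text does not describe.

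For a change score with equal variances before and after, R² = (1 − r)/2, where r is the pre-post correlation. This treats percent change approximately as a change score.

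| r | R² | Power, ρ = 0 | Power, AR(1) |
|---|---|---|---|
| 0.3 | 0.35 | 80% | 84% |
| 0.5 | 0.25 | 74% | 79% |
| 0.7 | 0.15 | 69% | 73% |

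**Step 5: how firm is the 69.4?** The chi-square 95% interval on 17 df is 69.4 × √(17/30.19) = 52.1 to 69.4 × √(17/7.564) = 104.1. At ρ = 0 the single-change SD is then 36.8 to 73.6, and unadjusted power runs from 85% down to 33%. The stated figure lies inside that range even before the covariate is counted.

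**The case for a change.** The strongest case for acting is that a definite power figure was printed without support, and that the fix is one sentence. The alternative readings of p = 0.02 do not rescue it by themselves. Treated as an unpaired test of 18 against 18, it gives an SD of 51.6 and 58% unadjusted. Unrounded values of 0.015 to 0.025 give 66% to 58% at ρ = 0. A paired t-test on the log ratio gives the same powers as on the percent scale, because power depends only on t and ρ. Loss makes things worse: applying the primary calculation's 15%, 15 × 0.85 = 12.75, about 13 evaluable per group, gives 55% unadjusted at ρ = 0.

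This stands as far as it goes: the crossover result alone does not establish more than 80%, and the text does not show what would. But it shows a figure without stated inputs, not a miscalculated one. The planners cited a published source that is not among these documents, and may have had an SD from it. The low values come mainly from the unadjusted test, which is not the planned one, and from positive ρ, which nothing in section 7.1 suggests. The target difference is named, since a similar change means +37% against −5%, and two-sided 0.05 appears in the preceding paragraph and is the natural reading.

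**Conclusion.** The concern does not call for a change. The >80% is possibly optimistic: under the planned ANCOVA, with ρ at or slightly below zero and pre-post correlations of 0.3 to 0.7, the back-calculation puts power at roughly 69% to 84%. It is not disproved, because it is met at ρ = 0 with R² of about 0.35 or more, or at ρ = −0.25 with R² of 0.25 (83%), and the uncertainty in the back-calculated SD is wide enough to cover it. All of this rests on reading p = 0.02 as a two-sided paired t-test and on assumed values of ρ and R².

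What remains is a missing detail about a planning figure. The comparison is exploratory, uses a subset of 30, does not drive the 54 randomized, and leaves the primary and secondary analyses untouched. Writing down the SD, R² and evaluable number, or dropping the sentence, would alter no analysis, result or conclusion. An analyst would judge the B:F result by its estimate and precision rather than by the planning power.
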